| RECIST | Response Evaluation Criteria in Solid Tumors |
| SAE | Serious Adverse Event |
| SAbr | Stereotactic ablative body radiotherapy |
| SBRT | Stereotactic body radiotherapy |
| SCCC | Simmons Comprehensive Cancer Center |
| scRNAseq | Single cell RNA sequencing |
| SGOT | Serum Glutamic Oxaloacetic Transaminase |
| SPGT | Serum Glutamic Pyruvic Transaminase |
| TRUS | Transrectal ultrasound |
| WBC | White Blood Cells |

STUDY SCHEMA**Primary Endpoint & Hypothesis**

- Percentage of Children Ages 3-7 Requiring General Anesthesia: We hypothesize that PROMISE will lead to a reduction in the percentage of patients **ages 3-7** who require general anesthesia during radiation treatment from **70%** (institutional historical control) to **30%**.

Secondary Endpoints

Secondary endpoints will be analyzed for those on trial treated with PROMISE vs. anesthesia.

- Patient/family-reported health quality of life (PedsQL 3.0 Cancer Module) and anxiety (mYPAS-SF).
- Workflow data: treatment time, average patient movement, and number of beam turn offs due to movement beyond threshold.
- Overall cost of treatment.

STUDY SUMMARY

| | |
|--|--|
| Title | Pediatric Radiation Oncology with Movie Induced Sedation Effect (PROMISE): A Phase II Clinical Trial to Safely Reduce Anesthesia Use |
| Short Title | PROMISE Clinical Trial to Reduce Anesthesia Use |
| Protocol Number | STU-2021-1005 |
| Phase | Phase II |
| Methodology | Single-arm, open label |
| Study Duration | 2 years |
| Study Center(s) | Single-center |
| Objectives | 
Primary: To decrease the total number of pediatric patients who require general anesthesia through the use of PROMISE.
 
Secondary:
 
 - To assess the impact that PROMISE has on patient/family anxiety and quality of life, treatment time and clinical efficiency, and overall cost. - To determine the average patient movement and beam stoppages with the use of PROMISE. |
| Number of Subjects | 30 |
| Diagnosis and Main Inclusion Criteria | Age 3-11 and planned to undergo radiation therapy. |
| Study Product(s), Dose, Route, Regimen | PROMISE: an audio/visual technology for children to focus on during each radiation treatment to prevent movement. |
| Duration of administration | PROMISE will be used for each fraction of radiation treatment; number of fractions will vary by patient depending on individual diagnosis and treatment plan. |
| Reference therapy | Institutional historical control of percentage of patients age 3-7 who required general anesthesia during radiation therapy. |
| Statistical Methodology | 
We hypothesize that PROMISE will lead to a reduction in the percentage of patients ages 3-7 who require general anesthesia use from 70% (historical control) to 30%. Using a two-sided exact binomial test with a significance level of 0.05 and power=80%, a sample size of 13 patients (ages 3-7) will be needed to detect this difference.
 
In our past experience, ~42% of children ages 3-11 (eligibility criteria) are between 3-7 years old, so 30 children total will be needed to enroll 13 who are between 3-7 years old.
 |

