9.2 Sample Size and Accrual

In order to detect a reduction in the rate of general anesthesia use in pediatric patients age 3-7 from the historical control of 70% to the hypothesized 30%, the total number of patients needed to achieve 84% power is 13, using a two-sided exact binomial test with a significance level of 0.05. Over the last two years (2018-2019) at the University of Texas Southwestern we treated 52 pediatric patients aged 3-11 who would be eligible for this study, so on average 26 patients/year. We estimate the ability to enroll the large majority (>80%) of patients who are eligible for this trial, and so we estimate enrolling 20 patients per year. Of these patients, ~42% are ages 3-7, so we estimate that 8-9 patients in our 3-7 age target range per year will be enrolled. Thus, we expect to enroll a total of 30 patients, of whom 13 will be ages 3-7, in ~1.5 years, with the total trial completed in ~2 years.

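### Enrolling 30 children aged 3-11 does not assure the 13 aged 3-7 that the primary test needs: the chance is about 51%, and average power is about 75-80%.

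*Combined protocol and SAP*

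**What the plan says.** In the Study Summary, the Number of Subjects is 30 and the eligible age range is 3-11. The Statistical Methodology row sets an 80% power target for a two-sided exact binomial test at 0.05, comparing 70% with 30%, and concludes that "a sample size of 13 patients (ages 3-7) will be needed to detect this difference". It then converts to total enrolment through the centre's own estimate that roughly two in five of the eligible children (about 42%) fall in the younger group. The step from that share to the total reads: "so 30 children total will be needed to enroll 13 who are between 3-7 years old".

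Section 9.2 repeats the calculation with the attained power: "the total number of patients needed to achieve 84% power is 13, using a two-sided exact binomial test with a significance level of 0.05". It projects 20 enrolled per year, 8-9 of them aged 3-7, and ends: "Thus, we expect to enroll a total of 30 patients, of whom 13 will be ages 3-7, in ~1.5 years". The whole trial is to finish in about two years.

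Neither place, nor the eligibility criteria in section 3, sets an age quota, a rule to continue until 13 children aged 3-7 are in, or an allowance for children who cannot be evaluated. Section 5.5 allows withdrawal at any time.

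**The concern.** The number that determines power is the count aged 3-7. The number the plan controls is the count aged 3-11. Between them stands only an approximate historical share, and the plan treats the expected yield as if it were the yield. With no margin above 13, any run of older children leaves the primary analysis short.

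The consequence is specific to a small single-arm trial with one primary hypothesis. If 30 children are enrolled and 10 to 12 are aged 3-7, a result that misses significance could reflect the age mix rather than the intervention, and no later analysis can supply the missing children.

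**Working it through.** **Inputs.** Null rate 0.70, alternative 0.30, two-sided exact binomial test, alpha 0.05, n = 13, stated power 84% (section 9.2) and target 80% (Study Summary); total enrolment 30 and share about 0.42 (both places); accrual 20 per year (section 9.2).

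**Step 1: reproduce n = 13.** Let X be the number of 13 children needing anesthesia.
- P(X ≤ 5 | 0.70) = 0.0182 and P(X = 13 | 0.70) = 0.0097. The attained two-sided alpha is 0.0182 + 0.0097 = 0.0279.
- X = 6 cannot be added: P(X ≤ 6 | 0.70) = 0.062.
- Power = P(X ≤ 5 | 0.30) = 0.8346, or 83.5%. This agrees with the stated 84%.
- n = 13 is the smallest size reaching 80%: n = 11 gives 79.0% and n = 12 gives 72.4%.

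**Step 2: yield from 30.** Let N be the number aged 3-7, with N ~ Binomial(30, 0.42). This assumes each enrolled child is independently aged 3-7 with that probability.
- Mean = 30 × 0.42 = 12.6.
- P(N ≥ 13) = 0.511, so P(N ≤ 12) = 0.489.
- P(N ≤ 10) = 0.220.
- For a share of 0.40, P(N ≥ 13) = 0.42; for 0.43 it is 0.56.

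**Step 3: power by number obtained.** The plan does not say which two-sided exact test it means. Two common versions are equal-tailed (0.025 per side) and minimum-likelihood (reject the outcomes least probable under the null, up to 0.05 in total). They agree from 10 to 13 and part at 14, where the equal-tailed boundary stays at 5 and the minimum-likelihood boundary moves to 6.

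| N aged 3-7 | P(N) | Equal-tailed power | Minimum-likelihood power |
|---|---|---|---|
| 10 | 9.5% | 65.0% | 65.0% |
| 11 | 12.5% | 79.0% | 79.0% |
| 12 | 14.4% | 72.4% | 72.4% |
| 13 | 14.4% | 83.5% | 83.5% |
| 14 | 12.7% | 78.1% | 90.7% |

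**Step 4: average power with 30 enrolled.** Sum P(N = k) × power(k) over all k.
- Share 0.42: 75.1% equal-tailed, 79.7% minimum-likelihood.
- Share 0.40: 72.4% and 77.5%. Share 0.43: 76.3% and 80.7%.
- Chance that power is below 80%, at share 0.42: 61.6% equal-tailed, 48.9% minimum-likelihood.

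**Step 5: accrual time for 13 aged 3-7.** The rate is 20 × 0.42 = 8.4 per year, so the mean time is 13 / 8.4 = 1.55 years. The 90th percentile of total enrolment needed at the current mix is 40 (P(N ≥ 13) is 89.7% at 39 and 91.7% at 40), or 40 / 20 = 2.0 years at a steady 20 per year. If arrivals also vary as a Poisson process, the 90th percentile is 17.78 / 8.4 = 2.1 years, where 17.78 is the 90th percentile of a gamma variable with shape 13.

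**The case against.** The best reply is that 13 is the target and 30 only a projection: section 9.2 calls 13 the number needed and says the team expects to enroll 30. No sentence orders enrolment to stop at 30. If accrual simply continued until 13 were reached, the problem would vanish. This reading is possible, but it is not written. The Study Summary gives 30 as the number of subjects, and section 10.5 requires the study to be conducted as described. Stating the rule is what is asked for.

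The second reply concerns size, and most of it stands. The 75% average belongs to the equal-tailed test; under the minimum-likelihood test the average is 79.7%, which practically meets the 80% target though not 84%. The 61.6% chance of power below 80% includes N = 11 and N = 14, where equal-tailed power is 79.0% and 78.1%. Those two account for 12.5 + 12.7 = 25.2 points, leaving about 36% for power below 78%.

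A reader might infer three stronger things that the documents do not support:
- That the sample size calculation is wrong. It reproduces.
- That 80% and 84% contradict each other. The first is the design target, the second the attained power at the smallest n that meets it.
- That 30 should have been 31, because 13 / 0.42 = 30.95. The share is approximate, and the difference is within its rounding.

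Type I error is also not at issue: the exact test controls it at whatever number is obtained.

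**Conclusion.** The concern holds as a missing accrual rule. With an open total of 30, the plan has about an even chance (51%; 42-56% for shares of 0.40-0.43) of reaching the 13 children its primary test needs. If it falls short, power is at most 79%. Averaged over the age mix, power is about 75% (equal-tailed) or 80% (minimum-likelihood), against a stated 84%.

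The right description is that the stated power is not assured. To say that it is not delivered goes too far, since exactly 13 children give 83.5%.

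The figures assume that 30 is a fixed total, that ages are independent with a share near 0.42, and that every child aged 3-7 is evaluable. The plan gives no non-evaluable rate, so none was applied; any such loss would lower the yield further.

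**What to change.** In the Study Summary (Number of Subjects and Statistical Methodology) and in section 9.2:
- Define the accrual target as 13 children aged 3-7 evaluable for the primary endpoint, and define evaluable.
- Close ages 8-11 at 17 (30 − 13), and continue ages 3-7 until 13 evaluable children are reached.
- Name the two-sided exact test version and give the success boundary of 5 or fewer of 13. The version matters if the count overshoots: at 14 the boundary is 5 under one and 6 under the other.

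This fixes power at 83.5%. The costs should be disclosed:
- Some children aged 8-11 are turned away, which departs from the intention in section 1.3 to offer PROMISE across ages 3-11.
- The total may slightly exceed 30 if unevaluable younger children are replaced.
- Accrual averages about 1.5 years, as planned, but the 90th percentile is about 2.0-2.1 years before treatment and the 30-day follow-up. That strains the 2-year study duration.

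A larger open total is an alternative. With 36 children the chance of at least 13 is 81%, and with 40 it is 92%, at 36 / 20 = 1.8 and 40 / 20 = 2.0 years of accrual. If the open cap of 30 is kept, restate power as about 75-80%, depending on the two-sided definition chosen.

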1.0 BACKGROUND AND RATIONALE

1.1 Disease Background

Pediatric Radiation Oncology:

Childhood cancers are the leading cause of death in children in the United States. Over 10,000 children are diagnosed annually^{1,2} and, each year, the disease claims more lives than asthma, cystic fibrosis, diabetes, and pediatric AIDS combined. Very little is known about childhood cancer prevention³, and the most common types include leukemias, lymphomas, and central nervous system tumors^{1,2}. Both pediatric cancer incidence and cure rates increased from 1975 to 2004, with cure rates increasing in part because of the advancements in radiation therapy^{1,4}. Some of the innovations that have improved both local tumor control and systemic spread include conformal radiotherapy, brachytherapy, proton beam therapy, and stereotactic radiosurgery⁵. For children with a diagnosis of cancer, radiotherapy is a main curative and palliative treatment modality often administered in combination with surgical resection and/or chemotherapy⁶. While radiation treatments are effective, they are also very intensive. The entire course of radiotherapy for a pediatric patient often consists of 25 to 30 fractions, lasting for 5 to 6 weeks.

General Anesthesia Use in Pediatric Radiation Oncology:

Due to the precise nature of radiation therapy, immobilization is crucial for treatment effectiveness and patient safety^{3,4,7}. For this reason, according to current standard radiotherapy practice most pediatric cancer patients under 7 years of age receive general anesthesia at each fraction to ensure that the patient remains still during the treatment. Almost all children under the age of three, the majority of children under 7, and even some children up to age 12 require general anesthesia⁷. Based on a study by Ntoukas, we estimate 70% of patients age 3-7 can avoid general anesthesia with the implementation of Pediatric Radiation Oncology with Movie Induced Sedation Effect (PROMISE)⁸, which is further described below.

General anesthesia reduction is important because, if a child requires general anesthesia, he or she may receive up to 30 episodes of general anesthesia in succession^{6,9,10}. This also means that, for the 6-week duration of radiotherapy, a child may never fully return to his/her baseline activity. More importantly, the excessive use of sedatives introduces many risks and side effects that, combined with chemotherapy, and cancer itself, can greatly affect the overall treatment experience for the children and their families¹⁰⁻¹². Multiple other factors associated with frequent anesthesia administration worsen the treatment experience, and would be immediately eliminated if general anesthesia was no longer needed. For example, fasting on a daily basis, a necessary part of the anesthesia process, is often difficult in the pediatric population and strains both the child and parents¹³. Currently, pediatric radiation visits last multiple hours because of the need for lengthy pre- and post- anesthesia care. These visits could easily be shortened to minutes if anesthesia were avoided. Lastly, the anxiety, stress, and fears both patients and families experience largely due to anesthesia administration would dissipate with its disuse¹⁴.

1.2 Study Agent(s)/Therapy(ies) Background and Associated Known Toxicities

PROMISE

Pediatric Radiation Oncology with Movie Induced Sedation Effect (PROMISE) is an interactive, incentive-based movie system that integrates with a video surveillance gating module (VisionRT) to help keep a children's attention and prevent him or her from moving during radiation treatment. This technology is being studied as an alternative sedation

solution for pediatric patients needing radiation treatment. There are no known or expected toxicities associated with PROMISE.

As part of the trial, patients will be attempted to have CT simulation scan and first radiation treatment(s) using PROMISE, with general anesthesia on standby should PROMISE be unsuccessful. The only toxicity that could be indirectly associated with PROMISE is if the child moves during radiation treatment and this results in radiation temporarily being delivered to the wrong target. However, PROMISE is integrated with the video surveillance gating module VisionRT, so that if the patient moves beyond predefined safety threshold, the beam will automatically stop, so this is not an event that would ever be expected to happen. This auto-beam off ability is a unique feature of PROMISE that is not seen in competing technologies.

If PROMISE is unsuccessful for a given patient, then standard of care general anesthesia will be used for that patient's radiation treatments.

Side Effects of General Anesthesia:

Studies have discovered a plethora of adverse effects of anesthesia that manifest in pediatric patients even after they are discharged from the hospital. These effects range from motor imbalance and restlessness to excessive sedation, which requires admittance to the emergency room¹¹. In a recent study, after a single episode of general anesthesia, 31% of patients exhibited motor imbalance, 23% experienced gastrointestinal effects, and 4% required medical advice after dismissal¹¹. Furthermore, 5% of the children did not return to baseline activity until the second day after the procedure¹¹. All effects were experienced after the patients had already been discharged from the hospital, meaning that they were able to meet the nationally recommended discharge criteria, but still were not functioning at a baseline level. Many pediatric cancer patients receive general anesthesia before every single fraction (essentially every 24 hours); for patients with six-week treatments, this translates to a minimum of 30 episodes of anesthesia over the course of 40 days. For small children, 24 hours may not be enough time to fully recover from the effects of anesthesia; thus, for the 6-week duration of radiotherapy, a child may never fully return to his/her baseline activity given the potential duration of the effects sustained from each administration.

Short-Term and Long-Term Risks of General Anesthesia:

Upon receiving general anesthesia, some patients may experience a paradoxical reaction^{15,16}, rendering them irritable and violent. This outcome is unpredictable and cannot be foreseen by anesthesiologists. If a patient exhibits this response, the sedation regimen must be recalculated using alternative sedatives. Other potential risks of anesthesia include primary failure, where the prescribed dose of the drug is not enough to elicit the desired state of consciousness for the patient, and secondary failure, where the effects wear off more quickly than expected and the patient unexpectedly awakes during treatment. Primary or secondary failure result in an undesired, heightened level of patient consciousness, referred to as anesthesia awareness^{17,18}. Not only have anesthesia awareness patients reported excruciating surgical pain upon premature arousal, but anxiety, PTSD, and sleep disturbances are frequently reported in the wake of such incidents^{17,18}. Even when anesthesia is successfully administered, the use of intubation for airway assistance is needed, possibly leading to a laryngospasm that can be fatal within a minute for children^{7,15,19}. Respiratory, cardiovascular, and gastric complications as well can be life threatening even when anesthesia is administered properly⁷. Propofol sedation, a commonly used pediatric radiation therapy anesthesia method, can produce a wide spectrum of side effects ranging from increased secretions to seizures¹⁵. The short-term risks associated with anesthesia grow exponentially with increased administration, possibly leading to anesthesia failure and/or a laryngospasm. Additionally, following several episodes of general anesthesia, there is a chance that the child may incur long-term permanent neurological damage²⁰⁻²². Neurological adverse

effects are currently being investigated. Although the long-term risks of repeated general anesthesia have not been thoroughly studied, there is consensus within the clinical community that repeated general anesthesia should not be used to children if possible.

Lowered Efficacy and Added Costs with General Anesthesia:

Daily rounds of general anesthesia can easily double the amount of time patient, parents, and medical staff (including anesthesiologists) spend in the hospital for administration and recuperation, making the process less efficient and increasingly expensive. For example, anesthesia costs average \$50,000 per child over a typical six week treatment, therefore a reliable alternative to general anesthesia would drastically and immediately decrease costs²³. Logistically, involvement of anesthesia is difficult. Radiation oncology suites are often stand-alone structures not located near or in major hospitals or academic centers, where anesthesia is more easily provided⁶. Because anesthesiologists are not normally on site in a radiation oncology suite, it creates obstacles in scheduling, transportation, and compensation. This problem is likely to worsen moving forward because radiation oncology suites are more frequently being built further from, not closer to, major hospitals or academic centers²⁴. Anesthesia care provided in pediatric radiation therapy oncology suite is also often less efficient and safe. Anesthesiologist may be accustomed to working in operating room suites, which compared to radiation oncology suites, are relatively more efficient and have safer facilities, equipment, and personnel²⁴. One such example is an anesthesiologist is not allowed in the radiation suite during treatment, which is not the case in a typical operating room^{3,6}.

Current Attempts to Minimize Anesthesia in Pediatric Oncology

Multiple options are being explored to minimize the use of anesthesia in pediatric radiation oncology with varying levels of success: music therapy plays music pre-selected by the patient during treatment^{3,25}; interactive intervention and psychoeducational therapy entails preparatory play therapy, interactive support, and behavioral modeling^{3,26-28}; psychological preparation prepares patients emotionally and mentally for the upcoming treatments^{3,29}. Electronic monitors working in concert with behavioral training display movies or cartoons to distract patients during treatment used to increase patient cooperation and avoid anesthesia^{3,28}. AVATAR, a similar device to PROMISE created by Stanford, has shown promising results. Stanford's study, published online January 11, 2020 reviewed 224 pediatric patients three years before and three years after AVATAR implementation. They found that more patients avoided general anesthesia for all ages; 73.2% before AVATAR implementation versus 63.4% after implementation. AVATAR use also demonstrated a reduction in treatment time per session by 38% and 326 fewer anesthesia sessions over a three year period, a total cost savings of roughly \$500,000³⁰.

1.3 Rationale

In pediatric neuroimaging studies, it is critical to keep children motionless during the long periods of scanning³¹⁻³⁴. Programmed feedback loops between movement and continued access to audio/video systems and mock MRI scanners have been used to train children to remain still during the scanning, using operant conditioning^{20,35-37}. Great success has been achieved. Patients under study were reported³⁵ meeting a movement criterion of 2 mm per second or less, during a 20-min simulated scan. Subsequently, these patients cooperated with actual MRI scans without sedation. One hundred percent task compliance³⁸ during fMRI scan was observed among pediatric patients who were trained with multiple-reward compliance tactics.

The successful results obtained in non-sedated pediatric neuroimaging techniques have inspired us to develop similar technologies to facilitate pediatric radiotherapy without repeated general anesthesia. We have developed and validated technologies to facilitate pediatric radiotherapy without general anesthesia, which we have called Pediatric Radiation Oncology with Movie Induced Sedation Effect (PROMISE). While other

audiovisual distraction techniques have previously been described, as outlined above, PROMISE is the first system that allows for real time monitoring of patient motion and automatic shutting off of the beam if the patient moves outside of defined parameters, activating a built-in safety mechanism. When video integration becomes available, the video will also shut off if the patient moves allowing for real time behavioral training that incentivizes patients not to move.

We propose implementing PROMISE for all children between ages 3-11 undergoing radiation treatment through a phase II clinical trial with the following workflow: 1) During the CT simulation scan, a training session will be conducted, where the child will learn to lie still with positive and negative feedbacks provided by our system for behavioral training. This session will also be used as a screening test to choose children suitable for PROMISE. Only children meeting the movement-requirements during the training session will be selected as candidates for the following non-sedated radiation treatment. 2) During the treatment, a child will watch an age-appropriate movie or video of his/her choice. A 3D surface imaging system will be used to monitor the motion of the child. If the motion exceeds any pre-defined positioning thresholds (e.g., conventional radiotherapy (CRT): 0.5 cm in translation movements and 2° in three rotational angles; stereotactic radiotherapy (SBRT): 0.15 cm and 0.5 degree), the treatment beam will be shut off and the movie will be paused. 3) Beyond threshold movements the child will be instructed with the effectiveness of movement control strategy. 4) If the child reverts to treatment position within a pre-defined temporal threshold (e.g. 1 minute), the treatment will be resumed with a continuing movie. 5) If the child cannot revert to the treatment position within a pre-defined time threshold/or the movement is beyond any pre-defined re-alignment threshold value (e.g., 1 cm / 5° in three rotational angles), the radiation beam and the movie will be turned off, the patient will be readjusted and the treatment will resume. 6) In any treatment fraction, PROMISE treatment will be ceased if according to the physician, excessive movement is compromising the child's safety. If the child is consecutively noncompliant with PROMISE treatments for two fractions, he/she will receive radiotherapy treatment with general anesthesia for all subsequent fractions, unless instructed by physician to re-attempt PROMISE.

This proposed PROMISE project offers several innovation features: 1) safer cancer radiotherapy modality for pediatric patients; 2) replacing repeated general anesthesia with behavioral training and motion monitoring to enable pediatric radiotherapy without sedation; 3) using a video/audio system and movies/cartoons for behavioral training; 4) using a 3D surface imaging system to monitor the patient motion and to provide negative feedback for operant conditioning. Our work success will lead to a novel radiotherapy modality for pediatric cancer patients with reduced risks and side effects, and also lowered cost and increased efficiency. Most children who currently need general anesthesia for radiotherapy will benefit from this new technology.

